5.5.2 Crenolanib is Active against Leukemic Cell Lines and Primary Blasts with FLT3-D835

Crenolanib not only inhibited phosphorylation of the wild type FLT3 receptor in SEMK2 cells, but also inhibited phosphorylation of the FLT3-D835Y TKD mutation in Ba/F3 cells transfected with vectors expressing FLT3-D835Y (Figure 5.3). The IC₅₀ of crenolanib against the D835Y, TKD mutation of FLT3 was found to be 8.8nM.

[figure not shown]

Figure 5.3. Activity of crenolanib against FLT3-D835Y mutation transfected in Ba/F3 cells (Unpublished, data on file).

In leukemic blasts from a newly diagnosed AML patient with the FLT3-D835V mutation, FLT3 phosphorylation was inhibited by crenolanib but was resistant to sorafenib and quizartinib (Figure 5.4).

[figure not shown]

Figure 5.4. Leukemic blasts with the FLT3-D835V mutation were incubated with 20nM of crenolanib (Cren) or sorafenib (Sor) In contrast to sorafenib, crenolanib was able to provide near complete (>90%) inhibition of phosphorylated FLT3.²³

5.5.3 Leukemic Blasts from Patients who Relapsed on FLT3 TKI Therapy Were Inhibited by Crenolanib

Leukemic blasts were obtained from a patient who had been treated with quizartinib and subsequently underwent an allogeneic transplantation. The patient's leukemic blasts had a FLT3/D835 mutation in the background of a FLT3/ITD mutation. Leukemic blasts obtained at the time of post-transplant relapse showed sensitivity to crenolanib in an MTT assay (IC₅₀ of 26nM); with no sensitivity to sorafenib (Figure 5.5).

[figure not shown]

Figure 5.5. In primary patient blasts, crenolanib was the most potent inhibitor against FLT3/D835 in comparison to sorafenib.²³

5.5.4 Phase I/II Clinical Studies of Oral Crenolanib Show that it is well absorbed and well tolerated

Crenolanib has been clinically evaluated as a single agent in a dose-finding and dose-ranging phase-I study with fifty nine patients treated and was found to have good oral bioavailability. Crenolanib was rapidly absorbed on an empty stomach with a median t_{max} ranging from 1 to 4 hours. The half-life of crenolanib in this Phase I trial was found to be between 13-16 hours.

As of 31 May 2013, one treatment related death has reported in 200 patients treated with crenolanib both as a single agent and in combination. This death occurred during phase Ib evaluation of crenolanib with docetaxel and axitinib in a patient with metastatic NSCLC and liver metastases who developed progressive liver failure and died. This death was classified as possibly related to study drug although progressive metastatic disease in the liver was not excluded.

The most frequent non-hematological grade 1/2 toxicities were diarrhea, nausea, and vomiting (Table 5.2). In patients with GIST, anemia was the most frequent grade 1/2 hematological toxicity associated with crenolanib treatment. Four patients required transfusion, though most of these patients had grade 1/2 anemia prior to treatment initiation. The most commonly reported all-causality events of severity Grades 3 or 4 have included LFT increase, anemia, and decreased lymphocyte count. All LFT abnormalities resolved to baseline or less upon discontinuation of crenolanib. The AML protocol recommends prophylactic antiemetics and anti-diarrheals as well as regular monitoring of hepatic enzymes.

Table 5.2. Incidence of treatment-related AEs occurring in \geq 5% of the study population treated with single agent crenolanib, data as of May 2013

	N	CI CTC Se	verity Gra	de	_	atients =
	GRADE	GRADE	GRADE	GRADE	TOTAL	%
Adverse Event	1	2	3	4	AEs	Patients
Nausea	86	19	2	1	108	63
Vomiting	85	10	4	0	99	55
Diarrhea	62	13	1	0	76	45
Alanine aminotransferase						
increased	32	9	7	2	50	23
GGT increased	33	14	13	3	63	21
Fatigue	16	12	2	0	30	18
Alkaline phosphatase						
increased	25	10	2	0	37	14
Anorexia	15	5	1	0	21	13
Aspartate						
aminotransferase						
increased	28	11	6	2	47	13
Lymphocyte count						
decreased	22	10	7	2	41	13
Headache	14	1	2	0	17	10
Anemia	8	6	4	2	20	10
Abdominal pain	11	2	2	0	15	10
Dyspepsia	7	4	2	0	13	10
Dysgeusia	11	3	0	0	14	9
Constipation	11	2	0	0	13	9
White blood cell						
decreased	16	4	1	0	21	8

Proteinuria	12	0	0	0	12	7
Edema limbs	11	2	0	0	13	6
Hypophosphatemia	10	0	1	0	11	6
Hypoalbuminemia	8	0	0	0	8	6
Periorbital edema	8	0	0	0	8	6
Serum amylase increased	4	3	0	0	7	6
Dizziness	7	0	0	0	7	5
Platelet count decreased	4	0	0	2	6	5

QT prolongation has been observed in only two patients treated with single agent crenolanib

Fifty nine patients were treated in the phase I single agent study of crenolanib. ECGs were obtained on all subjects at screening done in triplicate at 2 to 5 minute intervals. Baseline ECG was defined as the closest evaluations prior to the first dose of study drug. The summary of QTc at baseline and on-treatment was provided by overall and dose level for the mean, median, range (minimum, maximum) and the frequencies (n [%] of males with (i) QTc within 431 to 450 msec, (ii) QTc>450 msec; females with (i) QTc within 451 to 470 msec, (ii) QTc>470 msec. Of all subjects examined for ECG at baseline 50.85% had normal values and 49.15% had abnormal value. Using the Fridericia QTc correction criteria, at baseline, there were no females with >470 msec QTc interval, however 1 male subject reported to have a QTc interval of >450 msec. On study, 4 male subjects had a QTc interval between 431 and 450 msec and 2 female subjects had a QTc interval between 451 and 470 msec. Baseline and worst on study QTc (Fridericia correction) is given in Table 5.3. For the Bazett QTc correction, 2 male subjects had a QTc interval >450 msec at baseline and on study 6 male subjects had a QTc interval >450 msec. There were no female subjects with a OTc interval >470 msec at baseline however 1 female subject had a QTc interval >470 msec while on-study. Baseline and worst on study QTc (Bazett correction) is given in Table 5.3.

There were two grade 1 QT interval prolongations observed in the 59 patients treated, that resolved without need for study drug interruption. No grade 2/3/4 QT interval prolongation have been observed. The grade 1 QT prolongation was observed in 1/6 patients in the 200mg QD without food cohort and in 1/4 patients in the 60mg BID without food cohort. However no QT prolongation was observed in 280mg QD (N=7) and 340mg QD (N=5) without food cohorts and 60 mg BID (N=8) and 100 mg BID (N=12) with food cohorts.

Table 5.3. Summary of QTc (Fridericia correction (A) and Bazett correction (B)) both baseline and worst on-study.

Summary of QTc (Fridericia correction) Baseline and Worst On-Study Summary of QTc (Bazett correction) Baseline and Worst On-Study
Treatment Group: Over All

	Bas	seline		0n-Study		Bas	seline		0n-Stud
	(1	N=59)	(1)	I=59)		(1	N=59)	(1)	N=59)
QTc interval(msec)	n	(%)	n	(%)	QTc interval(msec)	n	(%)	n	(%)
Total (males)	29	(49.2)	29	(49.2)	Total (males)	29	(49.2)	29	(49.2)
Mean QTc	400	(42.12)	408	(15.2)	Mean QTc	418	,,,,,,,,,,,,,,,,,,,,,,,,,,,,,,,,,,,,,,,	432	,
Median QTc	398		408		Median QTc	413		428	
Min QTc	356		370		Min QTc	365		368	
Max QTc	459		448		Max QTc	489		481	
Total (females)	30	(50.8)	30	(50.8)	Total (females)	30	(50.8)	30	(50.8)
Mean OTc	402		411		Mean QTc	425		436	
Median QTc	400		413		Median QTc	429		437	
Min QTc	357		336		Min QTc	393		374	
Max QTc	449		457		Max QTc	460		497	
431-450 (males)	2	(3.4)	4	(6.8)	431-450 (males)	6	(10.2)	8	(13.6)
451-470 (females)	0		2	(3,4)	451-470 (females)	3	(5.1)	9	(15.3)
>450 (males)	1	(1.7)	0		>450 (males)	2	(3,4)	6	(10.2)
>470 (females)	0		0		>470 (females)	0		1	(1.7)

In the pediatric phase I study of crenolanib being conducted at St. Jude's Children Cancer Center (Memphis, TN) in children with gliomas, no episodes of QT prolongations have been observed to date.

Effect of crenolanib on c-kit and potential for myelosuppression

Crenolanib has Kd for c-kit of 78nM as compared to FLT-3 of 0.74nM and could potentially not inhibit c-kit at doses that are adequate to inhibit FLT-3. Crenolanib because of its lower affinity for c-kit may have a lower potential to cause delayed marrow recovery in patients with AML. No grade 3/4 myelosuppression solely attributable to drug has been seen in the adult patients with AML treated to date with crenolanib. In addition, no greying of hair has been observed in any patients treated till-date.

Because of the poor reported results in treating relapsed FLT3 mutant AML with standard salvage approaches, especially those with D835 activating mutation, this trial will evaluate the safety of crenolanib as reinduction therapy for such patients and allow continuation of therapy after receipt of allogeneic stem cell transplantation (HSCT) to determine overall efficacy for this poor risk group of patients.

6. Patient Eligibility

6.1 Inclusion Criteria

- Relapsed/refractory primary AML or AML secondary to antecedent hematologic disorder with an expected survival of 3 months or greater
- Patients must have tested positive for FLT3-ITD and /or other FLT3 activating mutations within < 60 day screening period age ≥18 years
- ECOG PS 0 2 (Appendix II)
- Adequate liver function, defined as total or direct bilirubin ≤1.5x ULN, ALT ≤3.0x ULN, and AST ≤3.0x ULN. Exceptions for ALT and AST restrictions will be made in the setting of documented liver involvement with leukemia
- Adequate renal function, defined as serum creatinine ≤1.5x ULN
- Recovery from non-hematological toxicities of prior therapy (including HSCT) to no more than grade 1 (except alopecia)
- Subjects should have received no antileukemic therapy (except hydroxyurea) prior to the first dose of crenolanib as follows: for 14 days for classical cytotoxic agents and for five times the t1/2 (half-life) for FLT3 inhibitors and antineoplastic agents that are neither cytotoxic nor FLT3 inhibitors (e.g. hypomethylating agent or MEK inhibitor). Refer to Appendix XVII for half-life information and drugs considered as FLT3 inhibitors for purposes of this trial.
- Negative pregnancy test for women of childbearing potential
- Able and willing to provide written informed consent
- Subjects who received crenolanib prior to and are within 30 to 90 days of receipt of a allogeneic stem cell transplant (HSCT) and have either no active GVHD where therapy has been initiated or GVHD where therapy has not been escalated within 14 days prior to start of study drug.

6.2 Exclusion Criteria

- Absence of FLT3 activating mutation
- <5% blasts in blood or marrow at screening
- Concurrent chemotherapy, systemic immunosuppressants, or targeted anti-cancer agents, other than hydroxyurea
- Patient with concurrent severe and/or uncontrolled medical conditions that in the opinion of the investigator may impair the participation in the study or the evaluation of safety and/or efficacy
- HIV infection or active hepatitis B manifested as hepatitis B surface antigen (hepBs Atg) positivity or hepatitis C manifested as hepatitis C antibody positive.
- For post HSCT, subjects within 29 days of an allogeneic transplant, and/or are on an unstable dose of
 immunosuppressive drugs for management or prophylaxis of GVHD or have escalated therapy for GVHD
 within 14 days of starting study drug, and/or have >/=Grade 2 persistent non hematological toxicity related to
 the transplant or did not receive crenolanib prior to HSCT
- Evidence of lack of engraftment if post allogeneic transplant

- Unable to swallow pills
- Major surgical procedures within 14 days of Cycle 1 Day 1 administration of crenolanib.
- Unwillingness or inability to comply with protocol

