1.1 Primary Objectives

- Overall response rate defined as Complete remission (CR) including incomplete blood count recovery (CRi)
- Duration of response

Protocol: ARO-004

• Progression-free survival

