8.1 Baseline Screening

- 1. Medical history (includes documentation of current medications and allergies)
- 2. Height, weight, vital signs ECOG Performance Status (Appendix II)
- 3. Pregnancy test for women of child bearing capacity
- 4. A complete history and physical, documentation of all disease, concomitant medications and performance status
- 5. CBC, platelet count, differential
- 6. Creatinine, total bilirubin, ALT, and AST
- 7. Bone marrow aspirate within 14 days preceding study drug initiation. Cytogenetics will be obtained prior to therapy (results from prior analysis can be used for this purpose, if done within 6-months of enrollment)
- 8. Evaluation of FLT3-D835, FLT3-ITD and other mutational status (if not done < 60 days preceding study drug initiation).
- 9. Baseline EKG assessment

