9.1 Response Criteria

Response criteria will be adapted from the International Working Group for AML.²¹ Responders are relapsed/refractory patients receiving study drug as reinduction therapy who obtain a CR, CRi, or PR, with or without cytogenetic response, hematologic improvements, and morphologic leukemia-free state. Briefly, criteria are as follows:

- 1. Complete remission (CR):
 - a. Peripheral blood counts:
 - i. No circulating blasts
 - ii. Neutrophil count $\ge 1.0 \text{ x} 10^9/\text{L}$
 - 111. Platelet count $> 100 \times 10^9 / L$
 - b. Bone marrow aspirate and biopsy:
 - i. ≤5% blasts
 - ii. No Auer rods
 - iii. No extramedullary leukemia
- 2. Complete remission with incomplete blood count recovery (CRi):
 - a. Peripheral blood counts:
 - i. No circulating blasts
 - ii. Neutrophil count $<1.0 \times 10^9/L$, or
 - iii. Platelet count <100 x10⁹/L
 - b. Bone marrow aspirate and biopsy:
 - i. < 5% blasts
 - ii. No Auer rods
 - iii. No extramedullary leukemia
- 3. Partial remission:

Protocol: ARO-004

- a. All CR criteria if abnormal before treatment except:
- b. \geq 50 % reduction in bone marrow blast but still \geq 5% or
- c. Marrow blasts <5% with persistent Auer rods
- 4. Morphologic leukemia-free state:
 - a. Bone marrow: ≤5% myeloblasts
- 5. Hematologic Improvement (HI):

Hematologic response must be described by the number of positively affected cell lines.

- a. Erythroid response (E) (pretreatment Hgb <11 g/dL)
 - i. Hgb increase by ≥1.5 g/dL
- **b.** Platelet response (P) (pretreatment platelets $<100 \text{ x} 10^9/\text{L}$)
 - i. Absolute increase of $\ge 30 \times 10^9/L$ for patients starting with $> 20 \times 10^9/L$ platelets
 - ii. Increase from $< 20 \times 10^9/L$ to $> 20 \times 10^9/L$ and by at least 100%
- c. Neutrophil response (N) (pretreatment ANC $<1.0 \times 10^9/L$)
 - i. At least 100% increase and an absolute increase $> 0.5 \times 10^9/L$

10. Statistical Considerations

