Exclusion (From 1. All min 2. <5 sc. let 3. Co tan that 4. Para an co into para ev	sion Criteria-All must be NO in IRB approved protocol) beence of FLT3 activating utation 5% blasts in blood or marrow at creening (i.e. only extra-medullary ukemia) oncurrent chemotherapy, or regeted anti-cancer agents, other an hydroxyurea. Intent with concurrent severe and/or uncontrolled medical conditions that in the opinion of the vestigator may impair the articipation in the study or the valuation of safety and/or efficacy	Yes		N/A	
Exclu (From 1. Al mi 2. <5 sc lei 3. Co tai tha 4. Pa an co in pa ev 5. In:	sion Criteria-All must be NO in IRB approved protocol) beence of FLT3 activating utation 5% blasts in blood or marrow at creening (i.e. only extra-medullary ukemia) oncurrent chemotherapy, or regeted anti-cancer agents, other an hydroxyurea. Intent with concurrent severe and/or uncontrolled medical onditions that in the opinion of the vestigator may impair the articipation in the study or the	Yes		N/A	

7.	Subjects who have had HSCT and are within 29 days of an allogeneic transplant, and/or have clinically significant graft-versus-host disease requiring systemic treatment or did not take crenolanib prior to HSCT.					
8.	Unwillingness or inability to comply with protocol					
9.	Major surgical procedure within 14 days of Cycle 1 of crenolanib					
10.	Evidence of lack of engraftment if post HSCT					
metl	I subject files must include supporting hod of confirmation can include, but is lts, subject self-report, and medical reco	s not lin	nited to, 1			
IV.	Statement of Eligibility					
This	s subject is [eligible / ineligible]	for part	cicipation	in the stu	dy.	
_	gnature: nted Name:			Date:		

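### The 5% marrow blast limits in section 9.1 conflict with each other and with the entry limit, so a marrow at exactly 5% has no single classification

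*Combined protocol and SAP*

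**What the plan says.** **Entry.** Section 6.2 and the synopsis exclude "<5% blasts in blood or marrow at screening". The checklist in Appendix I repeats the criterion and adds a gloss limiting it to extramedullary disease: "5% blasts in blood or marrow at creening (i.e. only extra-medullary ukemia" (some letters are lost in the public copy). Section 8.1, item 7, requires a "Bone marrow aspirate within 14 days preceding study drug initiation".

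**Response limits in section 9.1.**
- CR (item 1): marrow blasts ≤5%, no Auer rods, no extramedullary leukemia, "No circulating blasts", and neutrophil and platelet thresholds.
- CRi (item 2): marrow blasts <5%, with neutrophils or platelets below threshold.
- PR (item 3): a fall of at least 50%, described as "reduction in bone marrow blast but still" ≥5%; or marrow <5% with persistent Auer rods.
- MLFS (item 4): one condition only, "Bone marrow: ≤5% myeloblasts".

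**Who is a responder.** Section 1.1 gives the primary endpoint as "Overall response rate defined as Complete remission (CR) including incomplete blood count recovery (CRi". Section 9.1 describes responders as patients "who obtain a CR, CRi, or PR, with or without cytogenetic response, hematologic improvements, and morphologic leukemia-free state". Section 10.3.7 refers the primary endpoint back to 9.1. Section 10.1 plans 14 patients and rejects the null hypothesis if at least 2 respond.

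**The concern.** The limit that defines active disease at entry and the limits that define response should not share a value, and the response categories should exclude one another at that limit. Here 5% falls on both sides. The two components of the primary endpoint, CR and CRi, also use different marrow limits, although they are meant to differ only in blood counts.

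At stake is whether a borderline marrow is scored the same way by every site and by the analyst. Where CR and PR both apply, nothing in 9.1 says which takes precedence, and under section 1.1 the choice decides whether the patient counts. With a threshold of 2 responders, one such choice can settle the result.

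The word *or* in the entry criterion is a second, separate problem: it can be read in two ways that enrol different patients.

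**Working it through.** **1. The plan's own figures.** Section 10.1 quotes 8.61% type I error and 85.07% power for at least 2 of 14 responders at 15% and 30%. These do not reproduce. At 15%, 1 − 0.85^14 − 14 × 0.15 × 0.85^13 = 64.3%. At 30%, 1 − 0.70^14 − 14 × 0.30 × 0.70^13 = 95.3%. That is a separate matter. Only the planned 14 patients and the threshold of 2 are used below.

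**2. Overlap of limits.** Entry on marrow is the set ≥5%. CR and MLFS are the set ≤5%. They meet at exactly 5%. CRi (<5%) does not meet the entry set. PR (≥5% after a fall of at least half) meets CR at exactly 5%.

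**3. Classification at and below 5%.** The 12% starting value is illustrative. Any start of 5 / 0.50 = 10% or more gives the required fall; from 12% it is (12 − 5) / 12 = 58.3%. On-treatment rows assume no circulating blasts, no Auer rods and no extramedullary leukemia.

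| Patient | MLFS | CR | CRi | PR |
|---|---|---|---|---|
| Before first dose: marrow 5%, blood blasts ≥5% | yes | no (blood blasts) | no | no (no fall) |
| 12% to 5%, counts recovered | yes | yes | no | yes |
| 12% to 5%, counts incomplete | yes | no | no | no, if counts were abnormal before treatment |
| 12% to below 5%, counts recovered | yes | yes | no | no |
| 12% to below 5%, counts incomplete | yes | no | yes | no |

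The second row is a responder under section 1.1 if labelled CR and a non-responder if labelled PR. The third and fifth rows show the mismatch between CR and CRi: at 5% there is a CR category but no matching CRi category.

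**4. Readings of the entry criterion.** Reading A excludes a patient if either site is below 5%. Reading B, which follows the Appendix I gloss, excludes only if both sites are below 5%.

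| Marrow / blood blasts | Reading A | Reading B | MLFS at baseline |
|---|---|---|---|
| 5% / ≥5% | eligible | eligible | yes |
| 5% / none | excluded | eligible | yes |
| 3% / 8% | excluded | eligible | yes |
| 40% / 2% | excluded | eligible | no |

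**5. Size.** One patient is 1/14 = 7.1 percentage points and 1/2 of the required responders. One reclassification moves the observed result from 1/14 (7.1%, null not rejected) to 2/14 (14.3%, null rejected).

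**6. After the change.** With CR and MLFS at <5%, a marrow of 5% after a fall of at least half with recovered counts is PR only. CR and CRi share one marrow limit, and no marrow at or above 5% meets MLFS. The 3% / 8% patient under reading B would still meet MLFS at baseline, because MLFS has no blood condition. The baseline sentence in the fix is needed for that case.

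**The case against.** The strongest case against is that little of this reaches the primary endpoint.

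- **MLFS.** A reader might infer that MLFS at baseline inflates the primary response rate. The documents do not support that. Section 1.1 counts CR and CRi only. The responder sentence in 9.1 can be read as listing MLFS as something that may accompany CR, CRi or PR, and its verb implies attainment on treatment. What stands is that the sentence is unclear and no baseline condition enforces attainment.
- **CR at baseline.** This needs a marrow of exactly 5%, clear blood, adequate counts and reading B of the entry criterion. Under reading A the patient has at least 5% blood blasts and cannot be CR at entry. A reader might add that hydroxyurea could clear the blood. It is limited to 14 days in cycle 1, the first on-treatment marrow is at cycle 2 day 1, and CR still needs the neutrophil and platelet thresholds. The route is narrow.
- **CR versus PR.** A patient who stays at 5% cannot be PR. One who falls to 5% from 10% or more has improved, and if 9.1's wider responder list governs, both labels count. This stands in part: the tie changes the primary count only under section 1.1, but that is where the primary objective is defined.
- **Which limit is the outlier.** One could keep ≤5% and change CRi instead; section 8.7.2 also treats >5% marrow blasts as a sign of persisting disease. That would align CR with CRi, but leave the overlap with PR and with entry.
- **Old screening values.** A reader might infer that the screening marrow predates the last chemotherapy. The marrow is due within 14 days of first dose and classical cytotoxics must have stopped 14 days before it, so the marrow ordinarily follows them. Requiring eligibility on marrow alone, or a new timing rule, would change the population and is a trade-off rather than a correction.

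**Conclusion.** The inconsistency is real and should be fixed. As written, a marrow at exactly 5% can be eligible disease and MLFS before treatment. After a fall of at least half with recovered counts it is both CR and PR. With incomplete counts it is not CRi.

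The effect is bounded. On the marrow limits the overlap is the single value 5%, and the documents do not say how often it is reported. If it occurs, one patient is 7.1 percentage points and half of the required responders. A reader might go further and recompute the chance of passing the 2-of-14 rule with one guaranteed responder. The documents do not support such a figure: no patient is shown to be an automatic responder under CR plus CRi, and the starting probability would carry over the separate sample-size discrepancy in section 10.1.

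The conclusion assumes that the ≤ and < signs in 9.1 are as printed in the public text, which shows some reading noise, and that section 1.1 governs the primary endpoint.

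**What to change.** 1. In section 9.1, change the marrow limit in items 1.b.i (CR) and 4.a (MLFS) from ≤5% to <5%. This matches CRi, the PR boundary and the entry limit. Check the signs against the source document first.
2. Add to 9.1 that a category already met at baseline, judged on the screening marrow required by section 8.1, does not count as a response.
3. Separately, reconcile the blood-or-marrow wording in section 6.2 and the synopsis with the gloss in Appendix I, so that all three places admit the same patients. The sponsor should decide and state which reading is intended.

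The cost is wording in 9.1, 6.2, the synopsis and, depending on the reading chosen, Appendix I. No procedure, visit or sample is added. Items 1 and 2 leave eligibility unchanged. A patient reaching exactly 5% with recovered counts after a fall of at least half would be recorded as PR only, which should be accepted before any response is adjudicated.
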